6.12.5.4 Impact of Amantadine Usage

The number and percent of patients taking amantadine treatment during the study (if any) will be presented alongside concomitant medications. If amantadine usage is reported among >5% of patients, the impact of amantadine usage on the primary analysis will be explored. Any diary data collected after commencing amantadine treatment will be discarded and the primary analysis will be repeated for all patients in the FAS, excluding any values obtained after initiation of amantadine.

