Patients included in the study must be on stable antiparkinsonian medications for at least 30 days prior to first 24-hour patient home diary completion and during the study. Rescue medications such as Madopar dispersable and intermittent Apomorphine injections are allowed if prescribed PRN prior to study entry. Other medications considered necessary for the patient's safety and well-being may be given at the discretion of the Investigator.

All concomitant therapy used within the four weeks prior to the screening period and during the study must be recorded on the CRF.

Non-permitted concomitant medication:

Inbrija (levodopa inhalation powder) is not allowed as a rescue medication during the study. No other drug under investigation may be used concomitantly with the IMP.

Treatment with amantadine is not allowed within 6 weeks before completion of the first 24-hour patient home diary and during the study.

Available *in vitro* data indicate that CYP2D6 and CYP1A2 are the main enzymes involved in the metabolism of mesdopetam. However, the exact contribution from each of these two enzymes in the elimination is not known, and there may be a risk for significant increase of exposure when mesdopetam is used together with a combination of medications being strong inhibitors of CYP2D6 and CYP1A2 (see Table 1). Therefore, a combination of such inhibitors, i.e. a CYP1A2 strong inhibitor and a CYP2D6 strong inhibitor concurrently, should be avoided throughout the study. A CYP2D6 genotyping testing will be performed at Visit 4 (Day 56).

Mesdopetam and its two main plasma metabolites M1 (IRL902) and M2 (IRL872) have been shown *in vitro* to not be inhibitors of the main drug metabolizing CYP450 enzymes to a significant degree. Restrictions on concomitant medications being CYP450 substrates are therefore not considered necessary during the study.

Mesdopetam and metabolite M2 (IRL872) are also not inhibitors or substrates to a significant extent to main drug membrane transporters. Restrictions on concomitant medications being substrates or inhibitors of drug transporters are not considered necessary during the study.

Confidential	Version: 5.0	Page 38 of 74
Protocol: IRL790C005	Date: 5 Mar 2021	e

Isoenzyme (cytochrome P450)	Strong Inhibitors	
CYP1A2	ciprofloxacin, enoxacin, fluvoxamine, zafirlukast	A combination of a CYP1A2 inhibitor and a CYP2D6 inhibitor is not permitted during the study.

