14.2. Sample size/power calculation

140 patients (35 per group), are enough to demonstrate a treatment difference of 3 hours, pooled standard deviation 3.5, between a single dose level of active treatment and control (i.e. 2.5 mg, 5 mg or 7.5 mg mesdopetam vs placebo b.i.d.) for the primary endpoint with 92% power and type 1 error rate 0.05 (two tailed). The sample size calculation is based on an expected dropout rate of 10%. The Sponsor will evaluate the actual dropout rate after 70 randomized patients have completed Visit 3 (week 4) and can, if the dropout rate in the study is higher than expected, decide to increase the sample size to a total of maximum 154 randomized patients (+10%).

Confidential	Version: 5.0	Page 62 of 74
Protocol: IRL790C005	Date: 5 Mar 2021	C

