4 SAMPLE SIZE

Analysis of the Phase IIa study Efficacy and Tolerability of IRL790 in 74 PD patients with levodopa-induced dyskinesia (LID) on stable antiparkinsonian medication (NCT03368170) suggested that daily ON-time with troublesome dyskinesia decreased to an observed difference of approximately 1.6 hours (p=0.0274) among treated patients (n=39) versus placebo (n=36). Doseresponse analysis suggested a dose dependent effect with an observed difference vs. placebo around 4.6 h at the 7.5 mg dose. A pooled standard deviation of 3.2-3.3 hours was observed among the doses studied. This observed data provided the assumptions for the sample size calculation.

140 randomized patients (35 per group) are thought to be enough to demonstrate a treatment difference of 3 hours with pooled standard deviation 3.5, between a single dose level of active treatment and control (i.e., 2.5 mg, 5 mg, or 7.5 mg mesdopetam vs placebo b.i.d.) for the primary endpoint with 92% power using a hierarchical testing strategy, with key secondary endpoints tested using a truncated Hochberg procedure with truncation parameter γ equal to 0.7 for the 7.5 and then the 5 mg doses and a standard Hochberg procedure for the 2.5 mg dose to maintain control of the family wise error rate (FWER) at the nominal 0.05 level.

QMD Ref: Worldwide-TMP-ST-005-7.0 Effective: 12Aug2019	Governing QMD: Worldwide-SOP-ST-001	
Confidentiality Statement		
This document is the property of Worldwide Clinical Trials Inc. and may not be duplicated, copied, altered or removed from company without prior approval from Worldwide Quality Assurance or in compliance with Worldwide Standard Operating Procedures.		
REF: Worldwide-TMP-QA-001f-1.3	Page 11 of 49	

Worldwide Clinical Trials Controlled Quality Management Document		
WORLDWIDE CLINICAL TRIALS	Sponsor:	Integrative Research Laboratories Sweden AB
	Protocol Number:	IRL790C005
STATISTICAL ANALYSIS PLAN. PHASE 2-3-4		

The sample size calculation was based on an expected dropout rate of 10%, i.e., assuming 31 patients per group will provide evaluable data on the primary endpoint at Week 12. The actual dropout rate was evaluated by the Sponsor after 70 randomized patients had completed Visit 3 (Week 4) and due to a higher-than-expected dropout rate, it was decided to increase the sample size to 154 (+10%) randomized patients as permitted by the protocol.

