5 RANDOMIZATION

At the baseline visit (Visit 1, Day 1) patients will be randomized 1:1:1:1 to receive one of three doses of mesdopetam (2.5 mg, 5 mg, or 7.5 mg) or placebo b.i.d. based on the randomization schedule prepared by the unblinded statistician.

During the first week (Day 1 evening dose to Day 9 morning dose) a run-in phase with either 5 mg mesdopetam or placebo b.i.d. will take place, during which all patients allocated to mesdopetam will receive 5 mg mesdopetam b.i.d. and patients allocated to placebo will receive placebo b.i.d. The purpose of the run-in period with 5 mg b.i.d. is to allow for a one-week dose titration for patients randomized to 7.5 mg b.i.d. In a previous Phase 2a study most patients tolerated 5 mg b.i.d. At Visit 2 (Day 9), patients will receive mesdopetam 2.5 mg, 5 mg or 7.5 mg or placebo b.i.d., as randomized.

Randomization will be performed via a web-based Interactive Response System (IRS), using a dynamic balancing (minimization) algorithm. Randomization will be stratified by average (based on at least two valid home diaries) of <6 daily hours and \geq 6 hours of daily ON-time with troublesome dyskinesia at baseline.

During the one-week run-in phase, the IRS will ensure all patients allocated to mesdopetam treatment will receive 5 mg mesdopetam b.i.d., followed by the randomized dose during the treatment period. Patients allocated to placebo will receive placebo during the first week run-in and then continue placebo during the whole treatment period. Any dose reduction will also be managed through the IRS to ensure that blinding is maintained.

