6.12.1 Estimand

The main study estimand will follow the 'treatment policy' strategy to estimate the treatment effect of mesdopetam (2.5 mg, 5 mg, or 7.5 mg b.i.d.) compared to placebo b.i.d. (treatment) on the

QMD Ref: Worldwide-TMP-ST-005-7.0 Effective: 12Aug2019	Governing QMD: Worldwide-SOP-ST-001
Confidentiality	/ Statement
This document is the property of Worldwide Clinical Trials Inc. and may n prior approval from Worldwide Quality Assurance or in compl	1 1 1
REF: Worldwide-TMP-QA-001f-1.3	Page 27 of 49

Worldwide Clinical Trials Controlled Quality Management Document		
WORLDWIDE CLINICAL TRIALS	Sponsor:	Integrative Research Laboratories Sweden AB
	Protocol Number:	IRL790C005
STATISTICAL ANALYSIS PLAN. PHASE 2-3-4		

change from baseline to Week 12 (population-level summary) in average daily ON-time (hours) (variable) in patients with Parkinson's Disease exhibiting ON-phase dyskinesia, as defined by the inclusion/exclusion criteria (population) regardless of missing motor diary data, any permitted dose reduction, use of amantadine (if any), or discontinuation for any reason.

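### The trigger for the amantadine analysis is a pooled rate with no named denominator, so it does not track imbalance between a dose arm and placebo

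*SAP*

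**What the plan says.** Protocol 8.2 prohibits the drug: "Treatment with amantadine is not allowed within 6 weeks before completion of the first 24-hour patient home diary and during the study". Any use on study is therefore a deviation.

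SAP 6.12.1 sets a treatment-policy estimand whose target is the effect "regardless of missing motor diary data, any permitted dose reduction, use of amantadine (if any), or discontinuation for any reason". Diary data collected after amantadine starts therefore stay in the primary analysis.

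SAP 6.12.5.4, one of the supportive analyses, always reports how many patients took amantadine. It goes further only on a condition: "If amantadine usage is reported among >5% of patients, the impact of amantadine usage on the primary analysis will be explored". What then follows is specific: "Any diary data collected after commencing amantadine treatment will be discarded and the primary analysis will be repeated for all patients in the FAS", leaving out the values obtained after amantadine began. The section sets no criterion by arm, no criterion for a difference between arms, and no analysis set for the percentage.

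The relevant sizes are in SAP 4 and 5. The planned total was 140, 35 per group. After the dropout review "it was decided to increase the sample size to 154 (+10%) randomized patients as permitted by the protocol". Allocation is equal: "patients will be randomized 1:1:1:1 to receive one of three doses of mesdopetam (2.5 mg, 5 mg, or 7.5 mg) or placebo b.i.d".

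**The concern.** Each primary comparison sets one mesdopetam dose against placebo. Amantadine use can pull such a comparison away from what it would be on unchanged background therapy only to the extent that the two arms differ in use. A rate pooled over four arms does not measure that difference. It can stay low when all users are in one arm, and it can be exceeded when use is perfectly even.

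At stake is the one planned analysis that removes only the post-amantadine values and keeps everything else. If use is uneven but stays under the pooled limit, the report would carry no prespecified estimate of how much the result owes to those values. The sponsor would have to add one after seeing the data, or do without.

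**Working it through.** **Inputs**

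- Trigger: use in more than 5% of patients (SAP 6.12.5.4).
- Randomized total: 154, raised from 140 (SAP 4).
- Allocation 1:1:1:1 (SAP 5), so 154/4 = 38.5 per arm, or 140/4 = 35.

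**The plan's own figures.** SAP 6.12.5.4 gives the threshold but no patient count. The design figures do reproduce. With a 3-hour difference, SD 3.5 and two-sided 0.05, 31 evaluable patients per group give 92.1% power by the normal approximation (91.3% by the noncentral t), against the stated 92%. Then 31/0.9 = 34.4, rounded up to 35 per group, or 140 in all, and 140 × 1.1 = 154. These figures only confirm the arm sizes; power plays no further part here.

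**Largest number of users that does not trigger.** For denominator N this is the largest whole number k with k/N ≤ 0.05. If all k are in one arm, their share of that arm is k/(N/4).

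| N | largest k | k/N | k/(N/4) | (k+1)/N |
|---|---|---|---|---|
| 154 | 7 | 4.5% | 18.2% | 5.2% |
| 140 | 7 | 5.0% | 20.0% | 5.7% |
| 139 | 6 | 4.3% | 17.3% | 5.04% |
| 130 | 6 | 4.6% | 18.5% | 5.4% |
| 120 | 6 | 5.0% | 20.0% | 5.8% |

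The limit is 7 for any denominator from 140 to 159 and 6 from 120 to 139. The denominator could fall below 140 if the FAS is meant and at least 154 − 139 = 15 randomized patients are not in it.

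**What the trigger responds to at N = 154**

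- Seven users in one arm, none elsewhere: pooled 4.5%, a gap of about 18 percentage points between that arm and any other, not triggered.
- Four users in placebo, none elsewhere: pooled 4/154 = 2.6%, a gap of 4/38.5 = 10.4 points, not triggered.
- Eight users, two per arm: pooled 5.2%, no gap in counts between arms, triggered.

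**The same threshold within each arm.** One user is 1/38 = 2.6%, which does not trigger. Two users are 2/35 = 5.7%, 2/38 = 5.3% or 2/39 = 5.1%, which do. At these arm sizes two arms could then differ by at most one user without the check being run.

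**The case against.** The strongest reply is that nothing in the primary inference turns on this section. It is a supportive analysis, it does not enter the testing sequence in SAP 6.15, and the estimand keeps post-amantadine data deliberately. That stands. A reader might infer that uneven use below the threshold costs power on the 7.5 mg comparison or inflates its false-positive rate, and that a better trigger would repair this. The documents do not support that inference. The primary model uses the same data whether the repeat is run or not, and under a treatment-policy estimand, uptake that differs because of treatment belongs to the effect being estimated. The documents also give no size for amantadine's effect on the diary endpoint.

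A reader might also infer that an imbalance would go unseen. It would not. User counts are presented alongside concomitant medications, which SAP 6.3.6 and 6.9 tabulate by treatment group, with a separate table for anti-Parkinson drugs and a separate listing of non-permitted medications. The per-protocol analysis (SAP 6.12.5.1) is unconditional, and inadmissible medication is among its possible grounds for exclusion (SAP 6.1.3). SAP 6 also allows extra analyses if the data warrant them.

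This cover is partial. The tables show who took amantadine, not what it did to the estimate. The per-protocol exclusion is optional, is settled at blind data review, and removes whole patients, including their diaries from before amantadine, together with patients who have unrelated deviations. An analysis added after the data are seen is not prespecified.

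Finally, use should be rare. The drug is prohibited, its use is a ground for withdrawal (Protocol 7.4), and patients who stop early are scheduled only for the Visit 6 assessments, which include no diary (Protocol 10.13 and 10.14). Withdrawn users would therefore add few post-amantadine values. This also stands, and it keeps the point small.

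**Conclusion.** The point holds as a cheap improvement. The trigger in SAP 6.12.5.4 names no denominator and, read plainly, pools the four arms. With 154 randomized patients up to 7 users could be in one arm without the analysis being required (6 if the denominator is below 140), which is about 17% to 20% of that arm over the denominators checked. Eight users spread evenly would require it.

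The consequence is one prespecified supportive analysis that may be missing. Primary power, type I error and the order of testing are unchanged.

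Two assumptions matter. First, the pooled reading is an inference, because the text says only patients. Second, all users in one arm is a worst case. If use were unrelated to arm, 7 users would all fall in one named arm with probability (1/4)^7 = 0.006%, and in any single arm with probability 4 × (1/4)^7 = 0.02%. Smaller imbalances, such as four users against none, escape the trigger in the same way.

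**What to change.** In SAP 6.12.5.4, replace the condition so that the primary analysis is repeated without post-amantadine values whenever any FAS patient has diary values recorded after starting amantadine. If a threshold is preferred, apply it within each randomized arm: run the repeat when more than 5% of the FAS patients in any arm used amantadine. Either wording also settles the denominator.

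The cost is a sentence or two of SAP text and at most one more run of a model the plan already specifies. The downside is one extra supportive table, which may differ little from the primary result when use is rare. The repeat would remain a supplement to the treatment-policy analysis, since it answers a different question and does not correct it.

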6.13 Secondary Efficacy Analyses

All secondary efficacy analyses will be performed on the FAS for all dose levels of mesdopetam (2.5 mg b.i.d., 5.0 mg b.i.d., 7.5 mg b.i.d., and pooled) and placebo.

6.13.1 Key Secondary Analyses

6.13.1.1 Functional Impact of Dyskinesia, MDS-UPDRS Question 4.2

Change from baseline with mesdopetam compared to placebo in ON-phase dyskinesia will be assessed by MDS-UPDRS part 4 question 4.2 (Functional impact of dyskinesias).

MDS-UPDRS Question 4.2 will be completed at all in-person visits up to end of treatment. A shift table for the change from baseline in number and percent of patients rated in each score category (0 to 4) will be presented by treatment group and visit. Percentages will be based on the number of patients with non-missing score at baseline and post-baseline for the relevant visit. Descriptive statistics for the score as a continuous measure for observed values and change from baseline to each post-baseline visit will also be provided.

Change from baseline with mesdopetam compared to placebo in MDS-UPDRS Question 4.2 score will be analysed as a continuous variable using a MMRM, conducted in the same manner as for the primary analysis, and reported (including model estimates and line plot) as described in QMD Ref: Worldwide-TMP-ST-005-7.0 Effective: 12Aug2019 Governing QMD: Worldwide-SOP-ST-001

Worldwide Clinical Trials Controlled Quality Management Document		
WORLDWIDE CLINICAL TRIALS	Sponsor:	Integrative Research Laboratories Sweden AB
	Protocol Number:	IRL790C005
STATISTICAL ANALYSIS PLAN. PHASE 2-3-4		

Section 6.12.3. The analysis will be repeated using the modified stratification factor in the MMRM on the randomised dose group.

6.13.1.2 Disability Associated with ON-Phase Dyskinesia, UDysRS Parts 1b and 4 Sum Score

Change from baseline with mesdopetam compared to placebo in disability associated with ONphase dyskinesia will be assessed with the sum score of parts 1b and 4 of the UDysRS.

Descriptive statistics for the sum score of parts 1b and 4 and change from baseline by visit will be provided by treatment group. Change from baseline in the sum score of parts 1b and 4 will be analysed and reported (including line plots) in the same manner as for the primary analysis, as described in Section 6.12.3. The analysis will be repeated using the modified stratification factor in the MMRM on the randomised dose group.

6.13.2 Other Key Secondary Analyses

6.13.2.1 Average Daily OFF-Time (Hours)

Any observed changes in the average daily time spent in the OFF-state with mesdopetam compared to placebo will be evaluated. The change from baseline in average daily OFF-time (hours) by visit will be analysed and reported using the same MMRM approach as for the primary analysis, with Week 12 as the timepoint of interest.

The endpoint of interest will be the upper and lower bounds of the 95% CI for estimated difference in LS mean of OFF-time (hours) for mesdopetam dose levels compared to placebo. As the study is not powered to detect equivalence of mesdopetam treatment compared to placebo, the 95% CI will be provided for discussion only and no inference will be made.

6.13.2.2 Motor Symptoms of PD, MDS-UPDRS Part 2 (M-EDL) Total Score

Change from baseline with mesdopetam compared to placebo in motor symptoms of PD will be assessed with the total score obtained from Part 2 of the MDS-UPDRS (M-EDL).

Descriptive statistics for the M-EDL total score (0 to 52) and change from baseline by visit will be provided by treatment group. Change from baseline in M-EDL total score will be analysed and reported (including line plots) in the same manner as for the primary analysis, as described in Section 6.12.3.

QMD Ref: Worldwide-TMP-ST-005-7.0 Effective: 12Aug2019	Governing QMD: Worldwide-SOP-ST-001	
Confidentiality Statement		
This document is the property of Worldwide Clinical Trials Inc. and may not be duplicated, copied, altered or removed from company without		
prior approval from Worldwide Quality Assurance or in compliance with Worldwide Standard Operating Procedures.		
REF: Worldwide-TMP-QA-001f-1.3	Page 35 of 49	

Worldwide Clinical Trials Controlled Quality Management Document		
WORLDWIDE CLINICAL TRIALS	Sponsor:	Integrative Research Laboratories Sweden AB
	Protocol Number:	IRL790C005
STATISTICAL ANALYSIS PLAN. PHASE 2-3-4		

6.13.3 Other Secondary Analyses

6.13.3.1 ON-Phase Dyskinesia, Modified UDysRS Parts 1, 3 and 4 Sum Score

Change from baseline with mesdopetam compared to placebo in ON-phase dyskinesia will be assessed with the sum score of the modified UDysRS (parts 1, 3 and 4).

Descriptive statistics for the sum score of parts 1, 3 and 4 and change from baseline by visit will be provided by treatment group. Change from baseline in parts 1, 3 and 4 sum score will be analysed and reported (including line plots) in the same manner as for the primary analysis, as described in Section 6.12.3.

6.13.3.2 Time Spent with Dyskinesias, MDS-UPDRS Question 4.1

Change from baseline with mesdopetam compared to placebo in ON-phase dyskinesia will be assessed by MDS-UPDRS Question 4.1 (Time spent with dyskinesias).

MDS-UPDRS Question 4.1 will be completed at all in-person visits up to end of treatment. A shift table for the change from baseline in number and percent of patients rated in each score category (0 to 4) will be presented by treatment group and visit. Percentages will be based on the number of patients with non-missing score at baseline and post-baseline for the relevant visit. Descriptive statistics for the score as a continuous measure for observed values and change from baseline to each post-baseline visit will also be provided.

Change from baseline with mesdopetam compared to placebo in MDS-UPDRS Question 4.1 score will be analysed as a continuous variable using a MMRM, conducted in the same manner as for the primary analysis, and reported (including model estimates and line plot) as described in Section 6.12.3.

6.13.3.3 Analysis of All Active Doses Pooled Compared to Placebo

All active doses will be pooled into one mesdopetam dose group and will be analysed compared to placebo alongside the individual doses for each of the primary, secondary, and exploratory analyses.

QMD Ref: Worldwide-TMP-ST-005-7.0 Effective: 12Aug2019	Governing QMD: Worldwide-SOP-ST-001	
Confidentiality Statement		
This document is the property of Worldwide Clinical Trials Inc. and may not be duplicated, copied, altered or removed from company without prior approval from Worldwide Quality Assurance or in compliance with Worldwide Standard Operating Procedures.		
REF: Worldwide-TMP-OA-001f-1.3 Page 3		
Worldwide Clinical Trials Controlled Quality Management Document		
------------------------------------------------------------------	------------------	---------------------------------------------
WORLDWIDE CLINICAL TRIALS	Sponsor:	Integrative Research Laboratories Sweden AB
CLINICAL TRIALS	Protocol Number:	IRL790C005
STATISTICAL ANALYSIS PLAN. PHASE 2-3-4		

